## SUMMARY OF CHANGES

Protocol Date	Section	Change
1/12/2022		Initial IRB approval
4/14/2022 v.2	Cover page	Addition of Co-Investigators [name], [name], CNP Removal of Co-Investigators [name], [name]. Corrections to Funding and Agent information
	Protocol Summary	Added pancreatic cancer to objectives for clarity
	Abbreviations	Added IDS
	3.1	Updated blinding procedures
	3.4	Revised to align criteria for patient removal from study with Table 7.1
	6.1	Clarified that research blood draw is to take place before first dose of escitalopram/placebo. Corrected days FACT-Hep is completed Revised unblinding criteria to include Gr. 4 hyponatremia. Added: Patients who are unblinded before they complete all study visits will be asked to continue to have study-related phone calls with study staff and complete all study-related questionnaires.
	6.2	Added to second bullet: or patient inability to swallow escitalopram/placebo capsules,
	6.3	Clarified that long-term survival follow-up starts after Week 25
	7.1	Corrected name and email for Psycho-Oncology Provider
	Table 7.1	Added hyponatremia
	9.1	Revised to reflect new drug supplier information and changes to drug packaging
	11.1.1	Screening visit updated to include ECOG performance status. Week 1, Day 1 updated to include toxicity assessment.
	14.2	Correction made – added word “treatment”.
	Appendix II	Small revision to Pill Diaries made for clarity.

Protocol Date	Section	Change
8/31/2022 V2.1	Cover page	Updated version date. Updated study staff and made corrections to add staff who were erroneously not included or not removed when they left UH: Added [name], [name], [name]., [name], CNP Removed: [name], [name] CNP and [name]
10/21/2022 V3.0	Cover page	Update version date to 10/21/2022
	Section 6.1	The following line has been removed: “and the patient is being treated at UH Main campus”. This line no longer relevant as study procedures will take place at satellites.
	Study Calendar	Updated to remove the following footnote as this amendment allows patients to be enrolled and have study procedures at satellites: *Patients who receive chemotherapy at satellites sites are required to come to Main campus for D1, 15, 71 and End of Treatment visits to receive pills/return unused pills and to collect/return their pill diary.
11/07/2022 v4.0	Cover page	Updated version date to 11/07/2022
	Section 7	Table 7.1: The CTCAE grading reference ranges for hyponatremia have been corrected.
	Section 8	
Revisions are being made to clarify that only study related SAEs and AESI are to be recorded and reported. SAEs related to chemo are not entered into the Oncore database or reported on a MedWatch form. The following revision have been made to this section:
 
8.2.3 Adverse Event Evaluation changed:  From: The investigator or designee is responsible for ensuring that adverse events of interest (both serious and non-serious as defined in previous sections) observed by the study staff or reported by the subject that are determined to be related to escitalopram/placebo which occur after the initiation of escitalopram/placebo are fully recorded in the subject's medical record. Source documentation must be available to support all adverse events.
 
To: The investigator or designee is responsible for ensuring that all adverse events, (both serious and non-serious as defined in previous sections) observed by the study staff or reported by the subject that are determined to be related or possibly related to escitalopram/placebo which occur after the initiation of escitalopram/placebo are fully recorded in the subject's medical record and reported according to AE reporting policies of the IRB of record. Adverse events attributed to chemotherapy and/or underlying disease will not be recorded for this study. Source documentation must be available to support all adverse events.
 
8.4 Reporting Procedures for Serious Adverse Events changed

Protocol Date	Section	Change
		
From: For the purposes of safety reporting, all adverse events of interest will be reported that occur from the initiation of escitalopram/placebo on Day 1 until the Week 25 study visit. Adverse events of interest, both serious and non-serious, and deaths that occur during this period will be recorded in the source documents. All SAEs should be monitored until they are resolved or are clearly determined to be due to a subject's stable or chronic condition or intercurrent illness(es). Related AEs will be followed until resolution to baseline or grade 1 or stabilization.
 
To: For the purposes of safety reporting, all adverse events determined to be related or possibly related to escitalopram/placebo will be reported that occur from the initiation of escitalopram/placebo on Day 1 until the Week 25 study visit. Adverse events both serious and non-serious, and deaths that occur during this period will be recorded in the source documents and reported according to AE reporting policies of the IRB of record. All SAEs should be monitored until they are resolved or are clearly determined to be due to a subject's stable or chronic condition or intercurrent illness(es). Related AEs will be followed until resolution to baseline or grade 1 or stabilization.
 
8.4.1 SAE Reporting Requirements  Language was added to clarify that only SAEs related to escitalopram/placebo are to be reported.
 
8.5 SAEs and OnCore revised  From: All SAEs will be entered into OnCore.
 
To: All SAEs related or possibly related to escitalopram/placebo will be entered into OnCore.

	Section 8.3	
Revised to state that the SAE Report Form to be used for this study is the FDA Form 3500A (MedWatch for Industry Form FDA 3500A – Mandatory Reporting) This form can be found at the following link:
 
https://www.fda.gov/safety/medical-product-safety-information/medwatch-forms-fda-safety-reporting

## STUDY SCHEMA

## PROTOCOL SUMMARY

Protocol Number/Title	CASE6220: A Phase II, Randomized, Double-blind, Trial Comparing Escitalopram to Placebo in Patients with Resectable Pancreatic Cancer
Study Phase	II
Brief Background/Rationale	Anti-depressants have been shown to be beneficial in cancer patients. They reduce depressive symptoms and improve quality of life. Randomized trials have shown that antidepressants can reduce the development of depression in non-depressed patients with breast, melanoma and head and neck cancers. In this trial, we will test the role of anti-depressants in patients with localized pancreatic and periampullary cancer receiving neoadjuvant therapy. It has been shown that treating depression can impact survival in cancer patients. Additionally, depressed pancreatic cancer patients have a worse survival. Therefore, anti-depressants may also have implications for cancer treatment.
Primary Objective	Primary Endpoint(s)  To determine if patients with localized pancreatic and periampullary cancer have a decreased risk of depression with 12 weeks of escitalopram treatment.
Secondary Objective(s)	Secondary Endpoint(s)  To determine if patients with localized pancreatic and periampullary cancer have improved quality of life with 12 weeks of escitalopram treatment.
Correlative Objective(s)	Correlative Endpoint(s)  To collect serum, and tissue samples of metabolites related to serotonin metabolism, and determine if levels correlate with depression, quality of life, or benefit of escitalopram
Sample Size	46 patients including 23 patients in each arm (escitalopram and placebo)
Disease sites/Conditions	Localized pancreatic ductal adenocarcinoma or other periampullary adenocarcinoma (bile duct, duodenal, ampullary).
Interventions	Escitalopram or placebo for 12 weeks as follows: 2 weeks: 10 mg/day (1 capsule) 8 weeks: 20 mg/day (2 capsules) 2 weeks: 10 mg/day (1 capsule)

## ABBREVIATIONS

AE	Adverse Event/Adverse Experience
CCCC	Case Comprehensive Cancer Center
CFR	Code of Federal Regulations
CRF	Case Report Form
CTCAE	Common Terminology Criteria for Adverse Events
DSTC	Data, Safety and Toxicity Committee
DSMP	Data and Safety Monitoring Plan
FDA	Food and Drug Administration
GCP	Good Clinical Practice
HIPAA	Health Insurance Portability and Accountability Act
IDS	Investigational Drug Services Pharmacy
IRB	Institutional Review Board
N	Number (typically refers to participants)
NCI	National Cancer Institute
NIH	National Institutes of Health
PDA	Pancreatic Ductal Adenocarcinoma
PHQ-9	Patient Health Questionnaire
PI	Principal Investigator
QA	Quality Assurance
QIDS	Quick Inventory of Depressive Symptoms
SAE	Serious Adverse Event/Serious Adverse Experience
SOC	Standard of Care
UH	University Hospitals

## **1.0 Introduction**

### **1.1 Background Information**

The diagnosis of major depressive disorder (MDD) is typically made clinically according to the DSM-5 diagnostic criteria. The prevalence in the general United States population is 6% , and the lifetime risk is about 17% . The risk is in fact lowest in older patients, with a point prevalence around 1% in individuals over 65 years . Thus, the high rate of depression in patients with cancer is striking, particularly since it is so widely undertreated. The rate of depression in patients diagnosed with cancer is increased by 4-fold over the general population by some estimates, with a point-prevalence as high as 12% . This has major implications for patients and their families. The comorbid incidence of depression in cancer patients leads to worse survival, longer and more frequent hospitalizations, decreased treatment compliance, and worse quality of life . In most instances, depressive symptoms develop within the first year of a cancer diagnosis, yet, unfortunately almost 73% of eligible patients do not receive appropriate therapy. Other studies have demonstrated that almost all inpatients , and 50% of outpatients with cancer have undiagnosed depression . There is a growing body of evidence that targeted interventions in cancer patients can improve depressive symptoms and quality of life, including behavioral therapy  and antidepressants. Therefore, in light of the high risk of depression in cancer patients, the low risk of treatment, and the potential benefit of antidepressant treatment, there is a strong argument to be made in favor of broad depression screening. Even further, the evidence supports a line of investigation to examine the utility of anti-depression treatment as a new standard of care in patients with high-risk cancers. Herein, we propose testing the use of anti-depressants in all patients with localized pancreatic and related cancer, with the primary goal to prevent worsening depression at 12 weeks.

### **1.2 Rationale for Proposed Study**

A recent randomized study of patients with head and neck cancer offers pioneering insights into the potential benefit of this approach. Lydiatt et al. randomized 148 patients with head and neck cancer of varying stages to escitalopram (Lexapro, an SSRI, 20 mg/day, except 10 mg/day during week 1) or placebo. Patients were included in the study if they were not depressed or had mild depression at the start of treatment, as indicated by a QIDS-SR score < 11. There were minimal adverse effects in both treatment groups. Depression was more common at later time points in the placebo group compared to the treatment group (24% vs. 10%), and the benefit persisted in a multivariable analysis. Thus, the number needed to treat to prevent a single case of depression was just 7 people. Additionally, there was better quality of life noted in patients in the treatment group at every time point in the study, and as early as after 1 month of treatment. Based on this study, we will administer the same dose of study drug. We will administer escitalopram at 10 mg/day for 2 weeks, 20 mg/day for 8 weeks, and 10 mg/day for the final 2 weeks (ramp up and ramp down periods) for a total of 12 weeks.

Due to the fact that depression is more common in pancreatic cancer than any other cancer type (40% of patients), depression symptoms overlap with presenting signs and symptoms of pancreatic cancer, and depression screening is currently not standard practice for patients undergoing treatment for pancreatic cancer, the QIDS survey (nor any other tool) has been validated in the

pancreatic cancer population, we will include all patients with localized pancreatic cancer in this trial, regardless of depression score. **Importantly, patients noted to have either severe depression per the QIDS screen or suicidal ideation will be referred to a study psychiatrist for a more thorough evaluation and care plan with consideration of starting a second pharmacologic agent. However, these patients will continue on study in a blinded fashion taking placebo or escitalopram.**

We will look at QIDS scores at 12 weeks as the primary study outcome. We hypothesize that patients receiving escitalopram will have a lower rate of moderate (or worse) depression, compared to patients receiving placebo.

#### QIDS (Quick inventory of depressive symptomatology)

QIDS is a 16-item survey that addresses each of the nine symptom domains covered in the DSM-V criteria for Major depressive disorder (depressed mood, loss of interest or pleasure, concentration/decision making, self-outlook, suicidal ideation, energy/fatigability, sleep, weight/appetite change, and psychomotor changes). The tool is used both for depression screening, and to measure depression severity, and has been heavily validated against established surveys. Its effectiveness is proven. The tool is straight forward, and is administered in either a self-reported form (SR), or a clinician-rated (CR) form, and requires minimal training. The QIDS scores range from 0-27. Scores are interpreted as follows:

0-5	No depression
6-10	Mild depression
11-15	Moderate depression
16-20	Severe depression
21-27	Very severe depression

In this study, we will be using the QIDS to measure the rate of depression at each time point, with the incidence of worsening depression at 12 weeks as a primary outcome. Patients with a QIDS score  $\geq 16$  at any time point will be referred to a psychiatrist for a more thorough evaluation and consideration for additional therapy.

#### PHQ-9

This survey has just 9 questions with respect to the past 2 weeks of life, and each question is scored on a 4-point scale: not at all = 0; several days = 1; more than half the days = 2; and nearly every day = 3. Scores are added up to determine if patients have depression. The 9th question asks about suicidal ideation. The tool mirrors the 9 criteria in DSM V and has been extensively validated.

0-4	Minimal depression
5-9	Mild depression
10-14	Moderate depression
15-19	Moderately severe depression
20-27	Very severe depression

### FACT-Hep (Quality of life survey)

The fact scales are quality of life surveys that can be administered by patients or by clinician/coordinators as an interview. The FACT-Hep has 27 general questions, and 18 questions that are specific to hepatopancreatobiliary cancer, for a total of 45 questions. The general questions span four domains: physical, social/family, emotional, and functional well-being. It requires less than 10 minutes to complete and targets the 6th grade reading level. Answers are given in the form of a five-point Likert scale as follows: 0 (Not at all), 1 (A little bit), 2 (Somewhat), 3 (Quite a bit), and 4 (Very much). Points are re-calibrated and compiled, such that high scores indicate a higher quality of life (opposite to the grading scheme of QIDS or PHQ-9 where a high score reflects depression). The additional 18 questions in the FACT-Hep address a subscale to estimate hepatopancreatobiliary quality of life issues. From these 45 answers, several different scores can be computed, including a FACT-global score (G), a hepatobiliary cancer subscale (HCS) score, a FACT-Hep total score (a sum of the prior two scores), and a FACT-Hep Trial Outcome Score (TOI) which is a summary of the physical + functional + HCS scores. The FACT form has been validated for use in patients with advanced and localized pancreatic cancer.

### **1.3 Correlative Studies**

The serotonin theory of depression is supported through clinical experience. Selective serotonin reuptake inhibitors (SSRIs) remain the most common class of medicines used to treat depression. Mechanistically, these drugs increase serotonin levels at brain synapses. Tryptophan is the principal substrate for serotonin synthesis, and therefore, tryptophan breakdown may have biologic implications on clinical depression in patients with dysregulated tryptophan catabolism. We and others have demonstrated that the enzymes responsible for tryptophan metabolism are dysregulated in pancreatic cancer. Specifically, the enzymes that divert tryptophan into kynurenine and related metabolites are overexpressed, including IDO1, IDO2, and TDO (. This pathway effectively shunts tryptophan away from serotonin synthesis.

In this study, we will examine the expression of each of these tryptophan degrading enzymes in resected PDAs (25 of 46 patients in the trial are expected to have resected specimens for analysis). We will determine if a correlation exists between expression levels of these enzymes in the tumor and 1) depression at baseline, and 2) the development of depression in patients on trial. Additionally, plasma levels of specific tryptophan metabolites will be measured in patients at the start of treatment. Patients undergoing resection will have repeat levels taken 1-2 months after resection to determine how tumor burden impacts metabolite levels.

### **1.4 Potential Risks and Benefits**

The study drug, escitalopram, is FDA approved for the treatment of depression. It is safe and well tolerated.

#### **Potential Risks**

Adverse side effects include:

Nausea (15%)

Ejaculatory disorder (9%)  
Insomnia (9%)  
Diarrhea (8%)  
Dry mouth (6%)  
Somnolence (6%)  
Dizziness (5%)  
Hyperhidrosis (5%)  
Fatigue (5%)  
Rhinitis (5%)  
Influenza-like symptoms (5%)

## **Benefits**

Potential benefits of the study for the patient include prevention of depression, improved quality of life, and improved cancer survival. For the field, the study may demonstrate that prophylactic anti-depressant use is beneficial and provide a justification for a larger, phase III trial.

## **2.0 Objectives**

Anti-depressants have been shown in multiple studies to be beneficial in cancer patients . They reduce depressive symptoms and improve quality of life. Moreover, anti-depressants have been shown in randomized trials of breast cancer, melanoma, and head and neck cancer to reduce the development of depression in non-depressed cancer patients . In this trial, we will test the role of anti-depressants in patients with localized pancreatic and periampullary cancer receiving neoadjuvant therapy. It has also been shown that treating depression can impact survival in cancer patients . Additionally, depressed pancreatic cancer patients have a worse survival . Therefore, anti-depressants may also have implications for cancer treatment.

### **2.1 Primary Objective**

To obtain preliminary evidence of the efficacy of daily escitalopram in reducing depression in patients with localized pancreatic or periampullary cancer receiving neoadjuvant therapy. The primary endpoint will be a reduction in the rate of depression at 12 weeks using a QIDS survey.

### **2.2 Secondary Objectives**

- To determine depression rates in patients with resected pancreatic cancer at baseline and at 12 weeks.
- To determine if daily escitalopram improves the quality of life in patients with localized pancreatic and periampullary cancer.
  - To determine if daily escitalopram improves survival in patients with resected pancreatic cancer.
  - Study tissues and serum to determine if molecular markers of the serotonin-tryptophan-kynurene pathway are associated with depression scores.
  - Study tissues and serum to determine if molecular markers of the serotonin-tryptophan-kynurene pathway are associated with the efficacy of anti-depressants in patients with pancreatic cancer.

- Test for an association between tryptophan intermediates and immune profile in tumors and blood of patients with pancreatic cancer.

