### **3.1 Study Characteristics**

Patients may be non-depressed or depressed. Those who are severely depressed according to the Quick Inventory of Depression Survey (QIDS  $\geq 16$  points) will be referred to a psychiatrist for further evaluation and possibly additional therapy, based on clinical judgement. The study will be started at University Hospitals Cleveland Medical Center with the possibility that it can be opened at alternative sites if needed for patient accrual.

At the time of study enrollment, the treating physician must have the intent to treat the patient with 12 weeks of neoadjuvant chemotherapy as standard of care cancer treatment. For this study, patients will be randomized in a 1:1 ratio to receive escitalopram or placebo using a randomization table prepared by the study statistician. This randomization table will be shared by the statistician only with the Investigational Drug Services Pharmacy (IDS) personnel and will detail for all 55 patients/study IDs whether that patient is to receive escitalopram or placebo. Each patient will be

assigned a study number, in sequential order, only after all eligibility criteria have been confirmed by the study coordinator, treating physician (Investigator or Co-investigator) involved in the case, and by a member of the Clinical Trials Unit's Quality Assurance department.

It is possible that burden of disease could influence mood. Therefore, patients will also be stratified according to whether they have resectable disease or locally advanced disease (borderline resectable or unresectable) according to NCCN criteria. A pancreatic surgeon (PI or Co-Investigator) will determine this status using the Tumor Profile Assessment (see Appendix VIII). The Tumor Profile Assessment is to be filled out by the PI or by the Co-investigator prior to randomization.

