### **10.1.2 Rationale**

We will determine if a correlation exists between expression levels of these enzymes in the tumor and 1) depression at baseline, and 2) the development of depression in patients on trial. Additionally, serum levels (or plasma levels are a suitable alternative) of specific tryptophan metabolites will be measured in patients at the start of treatment. Patients undergoing resection will have repeat levels taken 1-2 months after resection to determine how tumor burden impacts metabolite levels.

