### 10.2.6 Methods

Collected tumors will be assayed for IDO1, IDO2 and TDO2 expression. We will test to see if expression of these enzymes correlate with depression scores or response to treatment.

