### Depression

The primary outcome is moderate or greater depression defined as a QIDS-SR score greater than 11. All patients will have localized disease, but be stratified by extent of disease: resectable vs. unresectable, based on imaging and as determined by the PI Based on the Tumor Profile Assessment. Under Generalized Linear Model (GLM) framework, a modified Poisson model can be constructed as the working model to directly estimate the relative risk of depression at each measurement time through 12 weeks (Zou and Donner 2013). Measurement time will be treated as a categorical/ordinal variable to allow for differing risk of depression in controls at each time point. The model will adjust for baseline QIDS-SR score as a continuous covariate and the stratification variable. Generalized Estimating Equation (GEE) will be used to account for correlation among the 6 repeated post-randomization measurements through month 3 for each participant. A time by randomization assignment interaction variable will be included to allow for estimation of the relative risk at each measurement time. The primary interest is to compare the two treatment groups at 12 weeks. This comparison will be performed at the one-sided alpha=0.10 level.

Since the GEE estimates are only valid under the Missing At Random (MAR) assumption if the working correlation structure is correctly specified, missing dichotomous outcomes will be imputed using Multiple Imputation (MI) prior to analysis (Li et al 2006). Estimates using this method are consistent under the MAR assumption (Beunckens et al 2008).

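### Marker-depression analyses specify only a simple correlation, so a blood metabolite-depression association could partly reflect disease burden

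*Combined protocol and SAP*

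**What the plan says.** Section 2.2 lists among the secondary objectives: "Study tissues and serum to determine if molecular markers of the serotonin-tryptophan-kynurene pathway are associated with depression scores". The Protocol Summary and Sections 1.3, 10.1.2, 10.2.2 and 10.2.6 describe the analysis only as a correlation. For tumor enzymes, Section 10.1.2 has: "We will determine if a correlation exists between expression levels of these enzymes in the tumor and 1) depression at baseline", followed by the development of depression on trial. Section 10.2.6 has: "We will test to see if expression of these enzymes correlate with depression scores or response to treatment". For serum levels, the Protocol Summary says only that they will be examined for correlation with depression, quality of life or benefit. No covariate is named in any of these places.

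Section 14.2 sets out analyses for QIDS, PHQ-9, FACT-Hep and survival, and none for markers. The primary QIDS model does account for extent of disease: "The model will adjust for baseline QIDS-SR score as a continuous covariate and the stratification variable". Survival is adjusted for staging with a stratified log-rank test.

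On burden, Section 3.1 explains the stratification with "It is possible that burden of disease could influence mood". Section 10.1.2 plans: "Patients undergoing resection will have repeat levels taken 1-2 months after resection to determine how tumor burden impacts metabolite levels". Section 10.1.3 is more guarded and asks whether burden has any influence on metabolite levels.

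**The concern.** Randomization protects the treatment comparison but not the comparison of patients with high and low marker levels, which is observational. If patients with more disease tend to have both different metabolite levels and worse mood, the two will correlate with no link between them. Sections 1.3 and 10.1.1 offer a mechanism, the diversion of tryptophan away from serotonin synthesis, so a positive correlation is likely to be read as support for it. The objective could then be answered yes on the strength of a burden effect. The plan already uses the relevant covariate in its primary model but does not carry it over to the analysis that needs it more.

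The post-resection blood sample does not close the gap. It exists only for resected patients, and the Study Calendar pairs no QIDS-SR with it.

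**Working it through.** **Plan's own figure.** There is none to reproduce. The documents give no sample size, effect size or significance level for the marker analyses, and the 80% power in Section 14.3 concerns the primary treatment comparison.

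**Inputs from the documents.** 55 patients randomized and 46 expected at 12 weeks (Section 14.3); 25 of 46 expected to have resected specimens (Sections 1.3, 10.2.2); Day 1 blood taken before dosing (Section 6.1; Study Calendar, footnote 2).

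**Assumptions.** A share p = 0.5 of patients is locally advanced; that status shifts marker and mood by d SD each, with within-stratum SD 1; there is no direct marker-mood link; the test is two-sided at 0.05.

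**Step 1: spurious correlation.** The common cause gives covariance p(1-p)d² and variance 1 + p(1-p)d² in each variable, so r = p(1-p)d² / (1 + p(1-p)d²).

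- d = 0.5: 0.0625/1.0625 = 0.06
- d = 0.75: 0.1406/1.1406 = 0.12
- d = 1.0: 0.25/1.25 = 0.20

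**Step 2: rejection rate with no direct link.** By Fisher's z, the statistic has mean m = atanh(r) × √(n-3), and the rate is P(Z > 1.96 - m) + P(Z < -1.96 - m).

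| d | r | m, n=55 | rate, n=55 | m, n=46 | rate, n=46 |
|---|---|---|---|---|---|
| 0.5 | 0.06 | 0.42 | 7% | 0.39 | 7% |
| 0.75 | 0.12 | 0.89 | 14-15% | 0.81 | 13% |
| 1.0 | 0.20 | 1.46 | 31% | 1.33 | 26% |

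Simulation agrees: 7%, 14% and 31% at n=55. The size depends on the assumed share. With p = 0.2 and d = 1.0, r = 0.16/1.16 = 0.14 and the rate at n=55 is about 17%.

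**Step 3: how far the stratum corrects this.** In Steps 1 and 2 the common cause is the stratum itself, so adjusting for it restores 5% by construction. A fairer test lets burden be continuous, correlated a with both marker and mood (so r = a²), and adjusts only for a two-level split. From 20,000 simulated trials per setting at n=55:

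| a | unadjusted | two-level split | continuous burden |
|---|---|---|---|
| 0.3 | 10% | 6% | 5% |
| 0.5 | 46% | 12% | 5% |
| 0.7 | 97% | 48% | 5% |

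For scale, r = 0.06 and 0.20 in Step 1 correspond to a = √0.06 = 0.24 and √0.20 = 0.45, so a = 0.7 is an extreme case. The split removes most of the inflation at moderate a, but not all of it.

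**Step 4: cost of adjustment.** The correlation detectable with 80% power is tanh((1.96 + 0.84)/√(n-3-k)) with k covariates. For k = 0, 1, 2 it is 0.535, 0.545, 0.556 at n=25 and 0.370, 0.373, 0.377 at n=55.

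**The case against.** Several counter-arguments have force.

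- **Silence is not a decision.** A reader might infer that the sponsor chose an unadjusted analysis. The word correlation sits in rationale and laboratory-method text, and Section 14 says nothing on markers. What stands is that no adjustment is specified, and that anyone following the text as written would run a simple correlation.
- **The premises are hedged.** A reader might infer that the protocol makes burden a common cause of marker level and mood. Section 3.1 calls the mood effect only a possibility, and Section 10.1.3 asks whether burden affects metabolites at all. Burden is a candidate confounder on the protocol's own terms, not an established one.
- **Tissue is not covered.** The burden statements concern blood metabolites. Nothing in the documents says that burden changes IDO1, IDO2 or TDO2 expression, so the rates above should not be carried over to the 25 specimens.
- **Tumor type is not a documented confounder.** Section 1.2 ranks pancreatic cancer first for depression and Section 1.3 reports enzyme dysregulation there, but no figure is given for bile duct, duodenal or ampullary tumors, which Section 4.1 also admits.
- **Arm cannot confound Day 1 serum.** Blood is drawn before dosing, so randomization makes it independent of arm. Adding arm mainly gains precision, even with the 40% v 13.8% rates assumed in Section 14.3.
- **The stakes are limited.** The objective asks about association, Section 2.4 lists biomarkers as exploratory endpoints, and no decision rule is attached. At a shift of 0.5 SD the inflation is only 7% against 5%.

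These points narrow the concern to serum and lower its weight. They do not supply a marker model or a reason to leave out a covariate already recorded.

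**Conclusion.** The concern holds for the serum metabolite-depression analysis. The plan states nothing beyond a correlation, while raising burden as a possible influence on both sides of it. Under the assumed 0.5 to 1.0 SD shifts with half the patients locally advanced, the nominal 5% test at n=55 rejects in about 7% to 31% of trials with no direct link; smaller shifts or a more uneven split give less. The shifts, the share and the 5% level are all assumptions.

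The documents do not support saying that burden is an established common cause, that tissue enzyme results are confounded by it, or that adjusting for the stratum would fully restore the error rate. This is a worthwhile correction to an exploratory analysis and does not affect the primary endpoint.

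**What to change.** - Add a marker paragraph to Section 14, and align Sections 10.1.2 and 10.2.6 with it: regress QIDS-SR on the marker, adjusted for the extent-of-disease stratum used at randomization (Section 3.1). Add randomized arm when the depression outcome is measured after Day 1.
- State that the two-level stratum is a coarse proxy for burden and that residual confounding may remain.
- Treat tumor type (pancreatic v other) as a sensitivity adjustment, or restrict the analysis to PDA.
- Reconcile Sections 1.3 and 10.2.2, which describe the 25 expected specimens as resected PDAs, with Section 10.2.3, which collects tumors from any patient undergoing resection.
- Label the results exploratory, in line with Section 2.4.

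The cost is SAP wording and one or two degrees of freedom. The stratum and arm are already recorded. At n=25, two covariates raise the correlation detectable with 80% power only from 0.535 to 0.556.
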